5.5. Study Population

5.5.1. Subject Disposition

Subject disposition, including the number of screened subjects, the number of subjects failed screening, the number of randomized subjects, the number of subjects who received study treatment in the TE, the number of subjects who received study treatment in the CE, who completed the study and the number of subjects who discontinued from the study, along with the reasons will be summarized by treatment group.

A listing of subject disposition will be generated, including the reason for premature study or treatment discontinuation, if applicable.

A listing of screen failure data will also be provided.

5.5.2. Demographic and Baseline Characteristics

Demographic and baseline characteristics, including age as collected, gender, race, ethnicity, and baseline BCVA (ETDRS letter score for both TE and CE), will be summarized for the Safety Population by treatment group using descriptive statistics.

5.6. Safety – Adverse events

A treatment-emergent AE (TEAE) is defined as an event that was not present prior to administration of the dose of study drug (ultevursen or sham-procedure) and present after the dose or if it represents the exacerbation of an event that was present prior to the dose.

Adverse events will be summarized by treatment group separately as follows:

- For non-ocular AE:
 - by subject, therefore, in any tabulation, a subject contributes only once to the count for a given adverse event (System Organ Class [SOC] or Preferred Term [PT]); and
 - During the overall study period (i.e., up to the last visit for the last subject).
 - Time to onset will be calculated in hours, relative to the last dose received, irrespective of which eye received the last dose (i.e., TE or CE).
- For ocular AE:

- by eye frequencies, separately for the TE and the CE, therefore, in any tabulation, an eye contributes only once to the count for a given AE (by SOC or PT). AEs that are reported in both eyes (i.e., OU) will be reported individually by eye in the tabular summaries; and
- During the overall study period (i.e., up to the last visit for the last subject).
- Time to onset will be calculated in hours, relative to the last dose received in the eye experiencing the ocular AE.

Unless otherwise stated, any summary of any type of TEAEs which includes the SOC and PT of the events will order the SOC and the PTs within the SOC by descending incidence of PT.

The following summary tables will be produced separately according to the type of AEs (ocular/non-ocular where applicable) as defined above:

- Overview of Ocular Adverse Events for Treatment Eye during the overall study period (Safety Population)
- Overview of Ocular Adverse Events for Contralateral Eye during the overall study period (Safety Population)
- Overview of Non-Ocular Adverse Events during the overall study period (Safety Population)
- Summary of Ocular Treatment-Emergent Adverse Events for Treatment Eye during the overall study period by MedDRA System Organ Class and Preferred Term (Safety Population)
- Summary of Ocular Treatment-Emergent Adverse Events for Contralateral Eye during the overall study period by MedDRA System Organ Class and Preferred Term (Safety Population).
- Summary of Non-Ocular Treatment-Emergent Adverse Events during the overall study period by MedDRA System Organ Class and Preferred Term (Safety Population).
- SAEs
- AESIs

5.6.1. Partial and Missing Date/Time for Adverse Events

Imputation of missing/partial AE date/time will be done only to identify TEAEs.

AE onset dates

- Partially missing onset date/time will be imputed as follows:

- When only Day is missing:
 - If Month & Year of the onset date are the same as Month & Year of the first administration date, the imputed onset date will be imputed as the minimum of the first administration date/time and the AE resolution date (imputed if needed).
 - Otherwise, the missing day will be replaced by “1.”
- When Day & Month are missing:
 - If Year of the onset date is the same as Year of the first administration date, the imputed onset date will be imputed as the minimum of the first administration date/time and the AE end date (imputed if needed).
 - Otherwise, the missing Day & Month will be replaced by “01 JAN.”
- If a partial AE start date is consistent with the actual start date being on Day 1, and either the AE end date information is completely missing, or the complete or imputed AE end date/time information indicates that the AE did not end before Day 1, the imputed AE start date will be Day 1 in the following scenarios:
 - The AE start time is missing (the AE will be flagged as treatment-emergent following the first dose of study treatment)
 - The AE start time is after the date/time of first dosing of study treatment on Day 1 (the AE will be flagged as treatment-emergent following the first dose of study treatment)
 - The AE start time is before the time of first dosing of study treatment on Day 1, and imputing the AE start date as Day 2 instead of Day 1 would be inconsistent with the partially recorded AE start date (e.g., the calendar month for Day 2 is not the same as for Day 1), or with the complete or imputed AE end date/time (in this case, the AE will not be flagged as treatment-emergent following the first dose of study treatment).
- Missing start time will be imputed with the time of administration if the day of AE start date and administration are identical, or with 00:00 otherwise.
- Completely missing onset dates for AEs will be imputed by the first administration date and the AE will be considered as treatment-emergent unless the end date/time of the AE (imputed if needed) or the end year of the AE (if day and month are missing) is entered and is before the first administration date. If the end date/time is before the first administration date, the AE will not be considered as treatment-emergent.

AE end dates

- If Day only is missing, incomplete end dates will be replaced by the last day of the month if it is not resulting in a date later than the date of the subject's last visit. In the latter case, the date of the subject's last visit will be used to impute the incomplete end date.
- If Day & Month are missing, Day & Month will be replaced by 31DEC if it is not resulting in a date later than the date of the subject's last visit. In the latter case, the date of the subject's last visit will be used to impute the incomplete end date.
- If the AE end date is completely missing, the AE will be assumed to be ongoing on the date of the subject's last visit and the incomplete end date will not be imputed.

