8.0 STUDY ASSESSMENT PROCEDURES

If a subject is unable to complete a specific assessment, this should be recorded in the eCRF and the subject's ability reassessed at the next specified visit. All attempts at performing assessments should be recorded. Any assessment may be repeated if the results are considered unreliable or of unacceptable quality by the Investigator.

All assessments will be conducted as indicated by the SOE

8.1 **Adverse Events**

Information regarding occurrence of AEs will be captured throughout the study. Duration (start and stop dates), severity/grade, outcome, treatment, and relationship to study drug will be recorded. Refer to Section 9.0, Assessment of Safety or Adverse Events and Serious Adverse Events, for further details.

8.2 **Laboratory Evaluations**

At Screening, laboratory results from the preceding QR421a study will be reviewed (if within the 12-week window), or a new local or central laboratory test, including a urine dipstick, will be performed to review for any abnormal laboratory values that may indicate a safety signal that would affect eligibility.

Subsequent laboratory evaluations will be conducted at a central laboratory and include serum chemistries, hematology and urinalysis. Reference ranges for all laboratory parameters are provided in the Laboratory Manual. See Appendix 2 for a list of laboratory tests to be conducted.

Serum chemistries will include sodium, potassium, chloride, bicarbonate, blood urea nitrogen (BUN), creatinine, glucose, calcium, phosphorus, alanine aminotransferase (ALT), aspartate aminotransferase (AST), gamma-glutamyl transferase (γGT), C-reactive protein (CRP), alkaline phosphatase (ALP), total and direct bilirubin, lactic dehydrogenase (LDH), albumin, and total

ProQR Therapeutics Page 36 of 65 protein. Estimated glomerular filtration rate (eGFR) is to be calculated using the CKD-EPI Creatinine Equation 2009 calculation.

Hematology will include a complete blood count (CBC): CBC with absolute differential (hematocrit, hemoglobin, white blood cell count [WBCs], red blood cell count, neutrophils, lymphocytes, monocytes, eosinophils, basophils, platelet count).

Coagulation panel: prothrombin time and International Normalized Ratio (INR).

Urinalysis (by visual inspection and dipstick) will include color and appearance, specific gravity, pH, protein, glucose, blood (erythrocytes), leukocytes, bilirubin, ketones, nitrite, and urobilinogen.

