9.0 ASSESSMENT OF SAFETY OR ADVERSE EVENTS AND SERIOUS ADVERSE **EVENTS**

All subjects who receive study treatment will be assessed for safety.

Investigators are responsible for monitoring the safety of subjects who have entered this study and for alerting the Sponsor regarding any event that seems unusual, even if this event may be

ProQR Therapeutics Page 38 of 65

considered an unanticipated benefit to the subject. The Investigator is responsible for appropriate medical care of subjects during the study and may add unscheduled visits, additional exams/tests for safety purposes.

9.1 Definitions of Adverse Event, Serious Adverse Event, and Suspected Unexpected **Serious Adverse Event**

9.1.1 **Adverse Events**

An AE is any untoward medical occurrence associated with the use of a drug in humans, whether considered drug related or not. Adverse events can include any unfavorable, noxious, unintended sign, symptom, or disease temporally associated with use of a study drug or other protocolimposed intervention, regardless of attribution. Adverse events may be spontaneously reported by the subject, discovered by Investigator questioning, or detected through laboratory test, or other means.

Adverse events include:

- Pre-existing medical conditions judged by the Investigator to have worsened in severity or frequency or changed in character during the protocol-specified AE reporting period (as specified in Section 9.3.1)
- Adverse events not previously observed in the subject that emerge during the protocol-specified AE reporting period (as specified in Section 9.3.1)
- Complications that occur as a result of protocol-mandated interventions
- Adverse events that occur prior to study treatment that are related to a protocol-mandated intervention (e.g., invasive procedures such as blood draws, sedation prior to IVT injection)

9.1.2 **Serious Adverse Events**

An AE or suspected adverse reaction is considered "serious" if, in the view of either the Investigator or Sponsor, it results in any of the following outcomes:

- Death
- Life-threatening AE. This definition implies that the subject, in the view of the Investigator, is at immediate risk of death from the event as it occurred. It does not include an event that, had it occurred in a more severe form, might have caused death
- Inpatient hospitalization or prolongs existing hospitalization, except for planned hospitalization

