9.3.1 Adverse Event Reporting Period

After signing of the Informed Consent all significant medical conditions including signs/symptoms of the underlying disease and known pre-existing medical conditions found during the screening period and up to initiation of dosing will be captured as medical history. This includes (ongoing) AEs from the preceding study. Any event/condition, including those related to participation in the study or study procedures, those not related to underlying disease or pre-existing medical conditions already part of medical history, and occurring before first dose of study treatment will be captured as a non-treatment emergent AE.

Any event/condition noted once the subject receives their dose of study drug will be captured as an AE. All AEs and SAEs regardless of attribution will be collected until at least 90 days following the last administration of study drug or the subject's EOS visit, whichever is later. At the last scheduled visit, the Investigator should instruct each subject to report to the Investigator any subsequent AEs/SAEs that the subject's personal physician believes could be related to prior study treatment.

SAEs unrelated to study treatment and non-serious AEs are to be followed until the last scheduled study visit (EOS visit), with the outcome at that point of time to be recorded in the eCRF. SAEs related to study treatment are to be followed until resolution or until they return to baseline, stabilize, or the subject is lost to follow-up. Resolution of AEs and SAEs (with dates) should be documented on the AE eCRF or paper AESI/SAE/Special Situation form (if applicable) and in the subject's medical record to facilitate source data verification. For some SAEs, the Sponsor or its designee may follow up by telephone, facsimile, electronic mail, and/or a monitoring visit to obtain additional case details deemed necessary to appropriately evaluate the SAE report (eg, hospital discharge summary, consultant report, or autopsy report).

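### SAP 5.6.1 checks by calendar day whether an AE ended before dosing, so an AE with no start time and a recorded end before the Day 1 injection can be classed as treatment-emergent

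*SAP*

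**What the plan says.** SAP 5.6.1 imputes incomplete AE dates and times solely to decide which AEs are treatment-emergent (TEAEs). Four of its rules matter here.

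- **Missing start time, dosing day:** "Missing start time will be imputed with the time of administration if the day of AE start date and administration are identical". The rule does not mention the AE's end.
- **Partial start date compatible with Day 1:** the first listed scenario reads "The AE start time is missing (the AE will be flagged as treatment-emergent following the first dose of study treatment". The condition on a known end is that it "indicates that the AE did not end before Day 1".
- **Only the day of onset missing, same month and year as the first dose:** onset becomes the "minimum of the first administration date/time and the AE resolution date (imputed if needed". A parallel rule covers a missing day and month.
- **Onset date completely missing:** the AE counts as treatment-emergent unless its end falls before the date of first administration.

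SAP 5.6 defines a new TEAE by two conditions: absent before the dose, and present after it. Protocol 9.3.1 says that an event "occurring before first dose of study treatment will be captured as a non-treatment emergent AE". It gives no rule for an event whose start time on the dosing day is unknown.

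**The concern.** Pre-injection events on Day 1 are foreseen. Protocol 9.1.1 lists among AEs "Adverse events that occur prior to study treatment that are related to a protocol-mandated intervention", and its examples are blood draws and sedation before the injection. Screening and Day 1 may be a single visit (Protocol 4.2.1.1), so procedures and first injection can share a date.

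An end check made at the level of the day cannot separate an event that was over before the injection from one that was still present after it, even when the end time is on record. For such a record the order is known. Treating it as treatment-emergent is then a misclassification and not caution. A programmer also meets two rules in the same section that can give opposite answers, with no stated order of precedence.

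At stake is the count of TEAEs in tables that SAP 5.6 specifies, and agreement between those tables and the protocol's own classification of pre-dose events.

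**Working it through.** The plan gives no figure to reproduce, so the check applies the written rules to test records. The times are assumptions for illustration: first injection on Day 1 at 10:00 and, where relevant, a recorded AE end at 09:00 the same day.

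| Record | Imputed start | Result under SAP 5.6.1 | Present after the dose (SAP 5.6)? |
|---|---|---|---|
| A. Day 1 date, start 08:00 recorded, end 09:00 | none needed | not treatment-emergent | no |
| B. Day 1 date, no start time, end on Day 1 without a time, or on Day 3 | 10:00 | treatment-emergent | yes, or cannot be excluded |
| C. Day 1 date, no start time, end 09:00 on Day 1 | 10:00 | treatment-emergent if judged on the imputed start | no |
| D. Month and year of onset only, no start time, end 09:00 on Day 1 | 09:00 or Day 1, depending on the rule | conflicting | no |
| E. Onset completely missing, end 09:00 on Day 1 | date of first administration | treatment-emergent | no |
| F. Day 1 date, start 11:00 recorded | none needed | treatment-emergent | yes |

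**Record C.** The imputed start is 10:00 and the recorded end is 09:00, so the AE starts 10:00 − 09:00 = 1 hour after it ended. The bullet imputes a time and does not itself set a flag. The flag follows only if the imputed start alone decides, and SAP 5.6 would then disagree.

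**Record D.** Two rules apply.

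- The minimum rule, reading the resolution with its recorded time, gives min(10:00, 09:00) = 09:00. This is before the dose, so the AE is not treatment-emergent.
- The Day 1 rule asks only whether the AE ended before Day 1. It ended on Day 1, so the check is passed, the start time is missing, and the SAP states that the AE is flagged.

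**Record E.** An end at 09:00 on Day 1 is not before the date of first administration, so the exception does not apply and the AE counts as treatment-emergent.

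**Records A, B and F** behave properly. A recorded pre-injection start on a complete date is left alone. An unknown order goes to treatment-emergent.

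The defect is therefore confined to C, D and E: start time missing, and a recorded end time on Day 1 before the injection. All three fail the SAP 5.6 requirement of presence after the dose, and in all three the event occurred before the first dose within the meaning of Protocol 9.3.1.

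Under the changes proposed below, C gets min(10:00, 09:00) = 09:00 and is not treatment-emergent. D and E are excluded because 09:00 is earlier than 10:00. A, B and F do not change.

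**The case against.** The strongest reply is that the TEAE definition in SAP 5.6 governs. An AE that ended before the injection is not present after it, so a careful programmer would exclude it whatever start time was imputed. This has force for record C. It does not dispose of D, where SAP 5.6.1 states the flag in words, or of E, where it says that the AE is considered treatment-emergent.

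A second reply is that the combination is unusual. Protocol 8.1 says "Duration (start and stop dates), severity/grade, outcome, treatment, and relationship to study drug will be recorded", naming dates and not clock times, but SAP 5.6 computes time to onset in hours and so expects times. If times are collected, most pre-injection starts will be recorded and need no imputation. If they are not, end times will be missing too and the problem record cannot be recognised. This stands, and it keeps the point small.

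Three stronger readings are tempting, but the documents do not support them.

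- A reader might infer that classing every untimed Day 1 event as treatment-emergent contradicts Protocol 9.3.1. It does not. That section covers events that occurred before the first dose and is silent on unknown times. Counting an unknown order as treatment-emergent is the usual conservative choice.
- A reader might infer that the SAP overrides a site's capture of an event as pre-dose. Nothing in SAP 5.6.1 says so. Whether the database holds a usable flag, and how programming would treat it, cannot be seen from the documents.
- A reader might infer that the primary endpoint is distorted. Protocol 4.1.1 defines it as the incidence and severity of AEs, not of TEAEs, and a pre-injection procedural AE is an AE either way. SAP 5.3.1 and SAP 6 base the listings on data as reported, so the recorded dates stay visible.

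**Conclusion.** The point holds in a narrow form. As written, SAP 5.6.1 gives a wrong or conflicting classification to an AE that has no start time and a recorded Day 1 end before the first injection. The cause is that the end is tested by calendar day and that the missing-time rule has no end check. For these records the section disagrees with itself, with SAP 5.6 and with Protocol 9.3.1.

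No effect size can be given. The documents report no AE counts and no rate of missing times, and the affected records are probably few. With the 20 subjects from PQ-421a-001, one subject is 1/20 = 5.0 percentage points of a subject-level incidence, but that is any one subject's share of the denominator and does not measure what this rule does. Ocular AEs are counted by eye and regimen group, so 20 is not the general denominator either.

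The conclusion assumes that an end time can be recorded when a start time is not, which SAP 5.6.1 allows for by referring to end date/time. Severity is low: a correction worth making, with no threat to the study's conclusions.

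**What to change.** Make three changes to SAP 5.6.1.

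1. Wherever an end time is recorded, compare the AE end with the date and time of the first dose, in place of the comparisons with Day 1 and with the date of first administration.
2. Impute a missing start time on a dosing day as the earlier of the administration time and the recorded AE end date/time. This extends the minimum logic that the section already uses for partial dates.
3. State that an AE that ended before the first dose is not treatment-emergent, and that this takes precedence over any imputed start.

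Keep the treatment-emergent default for AEs whose order relative to the dose is unknown, including those that ended on Day 1 with no end time.

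The cost is a few lines of text and a small programming change, which records C, D and E above can serve to test. No new data are needed.

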5.7. Other Data Listings to be Generated

The following by-subject data listings for the Safety Population will be provided:

- Subject Disposition
- Screen Failures (All Screened Subjects)
- Demographic and Baseline Characteristics (Safety Population)
- Non-Ocular Medical History (Safety Population)
- Ocular Medical History (Safety Population)
- Study Drug Administration of the TE (Safety Population)
- Study Drug Administration of the CE (Safety Population)
- BCVA Based on ETDRS (Safety Population)
- Low Luminance Visual Acuity (LLVA) (Safety Population)
- Spectral Domain Optical Coherence Tomography (SD-OCT) (Safety Population)
- Static Perimetry (Safety Population)
- Microperimetry (Safety Population)
- Ophthalmic exam (Safety Population)

- Non-Ocular Adverse Events (Safety Population)
- Ocular Adverse Events (Safety Population)
- Prior and/or Concomitant Medications (Safety Population)
- Laboratory results: Hematology, Coagulation, Chemistry and Urinalysis (Safety Population)

6. CHANGES TO PLANNED ANALYSES

As the study is prematurely stopped by Sponsor's decision, no formal statistical analysis will be produced. Only disposition, demographic and baseline characteristics, and overview of AEs will be summarized in tables. By-subjects data listings will be produced based on raw data.

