10.6 Subject Disposition, Demographics and Baseline Disease Characteristics

Subject disposition, baseline demographics and disease characteristics will be summarized for all subjects combined, and potentially grouped by baseline characteristics. Such grouping of subject disposition, demographics and disease characteristics by baseline characteristics will be described in the SAP.

10.7 **Treatment Compliance**

All doses are observed and administered by study staff. Treatment compliance will be determined by source records documenting treatment observations and summarized.

10.8 **Safety Analyses**

10.8.1 **Treatment Emergent Adverse Events**

A treatment-emergent AE (TEAE) is defined as an event that was not present prior to administration of the dose of study drug and present after the dose or if it represents the exacerbation of an event that was present prior to the dose.

Adverse events noted during the study will be coded to system organ classes (SOCs) and preferred terms (PTs) using the Medical Dictionary for Regulatory Activities (MedDRA) dictionary.

ProQR Therapeutics Page 48 of 65 The overall incidence of TEAEs will be classified by SOC and PT, and potentially summarized by groups based on baseline characteristics. Deaths, AE severity, seriousness, relationship to study drug will also be tabulated, potentially by groups based on baseline characteristics. If included, grouping based on baseline characteristics will be described in the SAP.

Ocular AEs will be presented separately for the study eye and the fellow eye.

10.8.2 **Other Safety Assessments**

Ophthalmology findings will also be summarized using descriptive statistics, frequencies, and percentages, and shifts from baseline, as appropriate. The number of subjects with a 10- and 15-letter decrease from baseline in BCVA will be tabulated.

10.9 **Systemic Exposure Analyses**

Systemic exposure will be estimated using standard methodology, if adequate serum concentrations of QR-421a are detected.

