2.2. Study Termination

In this context, the Analysis Description (AD) is abbreviated and describes the populations for analysis, data handling rules, statistical methods, and formats for data presentation that will be required for the close out of the study, after all subjects have completed the end of study visit and the database is locked.

The summary tabulations and listings that will be produced for the close out of the study, will provide the basis for the appropriate sections of the abbreviated clinical study report (CSR) or equivalent document.

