4. POPULATIONS DEFINITIONS

The following analysis sets will be evaluated and used for presentation and analysis of the data.

Analysis sets defined by eye will be respect to each eye. For example, the Safety Analysis Set for the CE will be determined by measurements taken on the CE. The subject-level analysis sets consist of subjects who meet the criteria in at least one of the eye-level analysis sets.

Screening Analysis Set: Includes all subjects who signed the informed consent form.

Safety Analysis Set (SAF): Includes all subjects/eyes who received at least one dose of study drug in Helia in either eye. Subjects/eyes will be analyzed according to their actual treatment. The SAF will be defined at the subject level or the eye level, depending on whether the endpoint is to be analyzed at the subject level or the eye level.

The disposition data will be presented for all screened subjects. The SAF will be the primary set for the analysis of the safety parameters. The SAF will also be used for descriptive summaries of demographics, baseline characteristics, and ocular/non-ocular medical history.

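### SAP 6 drops, without naming it, the count of 10- and 15-letter BCVA losses that Protocol 10.8.2 commits to tabulating

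*SAP*

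**What the plan says.** Protocol 10.8.2 contains two commitments of different strength. The general one is conditional: "Ophthalmology findings will also be summarized using descriptive statistics, frequencies, and percentages, and shifts from baseline, as appropriate". The specific one carries no condition. It covers the number of subjects with a 10-letter and a "15-letter decrease from baseline in BCVA will be tabulated".

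The SAP was written for close-out after early termination. SAP 2.2 states this openly: "In this context, the Analysis Description (AD) is abbreviated". SAP 6, the section on changes to planned analyses, then sets the scope of the tables: "Only disposition, demographic and baseline characteristics, and overview of AEs will be summarized in tables". Everything else becomes by-subject listings of raw data.

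BCVA is tabulated at one time point only. Under SAP 5.5.2, "baseline BCVA (ETDRS letter score for both TE and CE), will be summarized". After baseline it appears as one listing in SAP 5.7. Descriptive AE tables remain, by eye for ocular events; SAP 5.6 includes, for example, "Summary of Ocular Treatment-Emergent Adverse Events for Treatment Eye".

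**The concern.** Long-term safety is the primary objective (Protocol 3.1), and Protocol 2.3 names a fall in BCVA among the potential adverse events that monitoring should detect early. The letter-loss count is the one visual-acuity safety output that the protocol specifies by threshold. It rests on a measurement, so it does not depend on whether an investigator chose to record an event.

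The AE tables do depend on that choice. In the visible text, no number of letters lost makes a BCVA change an AE. Protocol 9.1.1 counts worsening of a pre-existing condition when the investigator judges that it has worsened. Protocol 9.2.1 grades severity by interference with usual function. Protocol 9.3.2 elicits events by non-directive questions. In an open-label study of a progressive retinal disease, a measured loss could be put down to the disease and not recorded. Such a loss would reach the report only as raw values in a listing.

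**Working it through.** No figure is stated or disputed, and the protocol gives no power calculation (Protocol 10.2 takes the sample size from the preceding studies). The check is a comparison of the protocol commitment with every output that the SAP names.

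1. **Required.** Protocol 10.8.2 asks for one count of subjects at two thresholds, 10 and 15 letters. I read these as losses of at least 10 and at least 15 letters.
2. **Tables planned.** SAP 5.5.1 gives disposition. SAP 5.5.2 gives demographics and baseline characteristics, including baseline BCVA. SAP 5.6 gives ocular AEs for the treated eye (TE) and contralateral eye (CE), non-ocular AEs, serious AEs and AEs of special interest. Tables containing a BCVA change or a letter-loss count: 0.
3. **Listings planned.** SAP 5.7 has one BCVA listing. SAP 5.3.1 and SAP 6 say that listings show data as entered, and no change from baseline or loss flag is specified.
4. **Is the omission declared?** In general terms, yes: SAP 6 is worded as an exhaustive list. The letter-loss count itself is not mentioned.
5. **Does the early stop prevent the count?** On the visible text, no. SAP 6 says that no formal statistical analysis will be produced, but a count of eyes over a threshold is descriptive. The protocol synopsis describes the analyses as generally descriptive from the start. SAP 2.2 places the outputs after the end-of-study visits and database lock, so the BCVA data collected will be in hand.
6. **Are the ingredients present?**
   - *Baseline:* yes. Protocol 4.2 sets it at Screening/Day 1 for both eyes.
   - *Denominator:* yes. SAP 5.4 uses column N, and SAP 4 defines the Safety Analysis Set at eye level as well as subject level. Its wording, "Includes all subjects/eyes who received at least one dose of study drug in Helia in either eye", should be applied eye by eye here, as SAP 4 says for eye-level sets.
   - *Unit:* yes. Each subject has one TE and one CE, so a count within either eye is still a number of subjects.
   - *Visit rule:* no. Neither document says which post-baseline value decides the matter (any visit, worst, last or confirmed). A restored table has to state this.
7. **Size.** The documents give no rate of BCVA loss and no number of eyes dosed. They mention 20 subjects from PQ-421a-001, which only indicates that the counts would be small. The number of losses not recorded as an AE cannot be estimated, and zero is possible.

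**The case against.** The strongest reply is that this is a declared economy in a close-out document. Protocol 10.1 leaves methodology and table formats to the SAP, and the SAP made the cut in the section meant for such changes. The opening words of SAP 2.2 refer to a context that is not shown, so a fuller reason may have been removed from the public copy. That stands. The sponsor's rationale cannot be called inadequate as a whole; it can only be said that the visible reason does not rule out a count.

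The practical loss may also be nil. A fall in BCVA is an expected AE, recorded losses are still tabulated, and the definition of AEs of special interest (Protocol 9.1.4) and the output shells (SAP 8) are not visible. With few subjects, a reader can count from the listing by hand. This also stands, and it limits the weight of the point. A hand count still leaves each reader to choose a visit rule, and the protocol promised a table.

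Third, the counts would be hard to interpret: no control group, a progressive disease, and study eyes that may carry exposure from PQ-421a-001. True, but the same limits apply to the AE tables that are kept.

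A reader might go further and infer that the SAP also breaks a promise by dropping shift tables for lens grade, inflammation or intraocular pressure. It does not, because that sentence of Protocol 10.8.2 is conditional. Nor is the baseline for the count unsettled. SAP 5.2 is brief and does not say whether it means the subject's or the eye's first dose, but Protocol 4.2 fixes Screening/Day 1 for both eyes.

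**Conclusion.** The concern holds as a minor one. A specific, unqualified safety count in Protocol 10.8.2 is dropped by SAP 6 without being named, and measured losses not recorded as an AE or AE of special interest appear only in a raw listing. The gap is one descriptive output at two thresholds. Its clinical size is unknown and may be zero.

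Two stronger conclusions are tempting, and the documents do not support them. One is that vision losses are being hidden: the reduction is stated openly, and all BCVA values are listed. The other is that the primary safety analysis is compromised: the primary endpoints are incidence and severity of AEs, and omitting the letter count does not affect them.

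The conclusion assumes that the separate output shells follow the restriction in SAP 6, and that the thresholds mean losses of at least 10 and at least 15 letters.

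**What to change.** In SAP 6, add one sentence keeping one descriptive table: n/N with a BCVA loss of at least 10 and at least 15 letters from the Screening/Day 1 baseline of Protocol 4.2, shown both at any post-baseline visit and at the last visit, for TE and CE separately, among eyes actually dosed in Helia, with no testing. Giving both visit rules supplies the definition that the documents lack: the first shows whether a loss ever occurred, the second whether it was present at the end. If the sponsor prefers not to produce the table, SAP 6 should at least name the Protocol 10.8.2 count as dropped and say why.

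The cost is one table shell run for each eye from data already collected, with no extra visits, assessments or patients. The downside is a longer abbreviated report, with small, uncontrolled counts in a progressive disease and earlier exposure in some study eyes. A footnote should say so.
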